3.2. Study Duration for Subjects

The Screening Period will start from the time of obtaining informed consent/assent and last no more than 28 days, at which time the Treatment Period will begin (Cycle 1 Day 1, first day of actual study drug administration). Each subject shall receive treatment for up to 24 cycles or until documented PD, consent/assent is withdrawn, treatment becomes intolerable, or death, whichever occurs first. Once treatment has been discontinued, subjects will enter into a Follow-up Period with phone call/clinic visit every 3 months (\pm 14 days), for up to 5 years from enrollment of the last subject, unless consent/assent is withdrawn, the subject is lost to follow-up, or death.

Stage 1 portion of the study is expected to last up to approximately 18 months prior to reaching the decision point. The Stage 2 portion of the study is expected to last up to approximately 27 months should all strata enroll the maximum number of subjects and assuming no subjects are replaced.

3.3. End of Trial

The End of Trial is defined as either the date of the last visit of the last subject to complete the post-treatment follow-up, or the date of receipt of the last data point from the last subject that is required for primary, secondary and/or exploratory analysis, as prespecified in the protocol, whichever is the later date.

4. STUDY POPULATION

4.1. Number of Subjects

The study population will consist of children and young adults aged 1 to < 21 years with recurrent or progressive primary brain tumors after at least one prior standard therapy, in 1 of 4 primary brain tumor types: high-grade glioma, medulloblastoma, ependymoma and DIPG. Eighty subjects (36 subjects in Stage 1 and 44 subjects in Stage 2) will be included should all strata enroll the maximum number of subjects and assuming no subjects are replaced. Approximately 80% of subjects across all strata will be < 17 years of age.

4.2. Inclusion Criteria

Subjects must satisfy the following criteria to be enrolled in the study:

1. Subject is 1 to < 21 years of age at the time of signing the ICF/IAF.
2. Subject (when applicable, parental/legal representative) must understand and voluntarily sign an ICF/IAF prior to any study-related assessments/procedures being conducted. Note: Adult individuals who lack capacity to consent for themselves will be excluded from the study.
3. Subject has received at least one prior standard therapy (or generally accepted upfront therapy if no standard exists) and have no known curative therapy.
4. Subject has a diagnosis of high-grade glioma, medulloblastoma, ependymoma or DIPG that is recurrent or progressive with the primary location in the CNS. Subjects with neurofibromatosis type 1 (NF-1) associated tumors are eligible if they meet all other eligibility criteria.
5. Subject has histological verification of tumor either at the time of diagnosis or recurrence. Subjects with DIPG are exempt from histologic verification if they have typical MRI findings of DIPG (ie, hypo- or isointense on T1-weighted imaging, hyperintense on fluid-attenuated inversion recovery (FLAIR) or T2-weighted imaging, epicenter in the pons, > 50% of pons involved).
6. Subject has measurable disease (including subjects that have undergone a surgical resection prior to enrollment), defined as a primary brain tumor that is measurable in 2 perpendicular diameters on MRI. For a lesion to be considered measurable, it must be at least twice the slice thickness on MRI (ie, visible on 2 or more axial slices).

Note: MRI should be performed with cuts of 3 mm or less in slice thickness contiguously. Further details regarding MRI acquisition requirements are outlined in the Imaging Manual.

7. To document the degree of tumor at study baseline, the following scan(s) must be obtained:
 - A brain MRI for all subjects with and without contrast (ie, gadolinium) and a spine MRI with contrast (ie, gadolinium) within 21 days prior to first dose of study treatment. For subjects on steroids, baseline MRI scans must be performed while on stable or decreasing dose of steroids for at least 5 days.

8. Subject has Karnofsky (age ≥ 16 years) or Lansky (age < 16 years) performance status score ≥ 50 at screening ([Appendix D](#)).
9. Subject has adequate bone marrow function defined as:
 - Peripheral ANC $\geq 1000/\text{mm}^3$
 - Platelet count $\geq 100,000/\text{mm}^3$ (transfusion independent defined as no platelet transfusion within 7 days and recovery from nadir)
 - Hemoglobin ≥ 8 g/dL (red blood cell [RBC] transfusion is allowed)
10. Subject has adequate renal function defined as:

Serum creatinine based on age/gender as described in [Table 3](#). Subjects that do not meet the criteria but who have a 24-hour creatinine clearance or radioisotope glomerular filtration rate (GFR) (radioisotope or iohalamate) ≥ 70 mL/min/1.73 m² are eligible.

Table 3: Serum Creatinine by Age and Gender

Age	Maximum Serum Creatinine (mg/dL)	
	Male	Female
1 to <2 years	0.6	0.6
2 to <6 years	0.8	0.8
6 to <10 years	1	1
10 to <13 years	1.2	1.2
13 to <16 years	1.5	1.4
≥ 16 years	1.7	1.4

The threshold creatinine values in this table were derived from the Schwartz formula for estimating glomerular filtration rate ([Schwartz, 1985](#)) utilizing child length and stature data published by the Centers for Disease Control.

11. Subject has adequate liver function defined as:
 - Total bilirubin ≤ 1.5 X upper limit of normal (ULN) for current age (≤ 3 X ULN if increase in bilirubin is attributable to Gilbert's Syndrome)
 - Alanine aminotransferase (ALT) (SPGT) is ≤ 3 X ULN for age
 - Serum albumin ≥ 3 g/dL
12. Subject has adequate pulmonary function defined as:
 - No evidence of dyspnea at rest
 - A pulse oximetry $\geq 93\%$
13. Subject has recovered from clinically significant acute treatment related toxicities from all prior therapies. Recovery is defined as a toxicity Grade ≤ 2 (common terminology criteria for adverse events [CTCAE] v. 4.03).
14. Subject has no significant worsening in clinical status for a minimum of 7 days prior to first dose of study drug.

15. Subject (and when applicable, with parental/legal representative) is willing and able to adhere to the study visit schedule and other protocol requirements.
16. Females of childbearing potential (FCBP), female children of childbearing potential (FCCBP), and male subjects who have reached puberty (and when applicable, with parental/legal representative) must agree to undergo physician-approved reproductive education and discuss the side effects of the study therapy on reproduction.
17. All subjects and/or parents/legal representative must have an understanding that pomalidomide could have a potential teratogenic risk. Female children of childbearing potential, defined as females who have achieved menarche and/or breast development in Tanner Stage 2 or greater and have not undergone a hysterectomy or bilateral oophorectomy and FCBP, defined as a female who has achieved menarche at some point, not undergone a hysterectomy or bilateral oophorectomy and has not been naturally postmenopausal for at least 24 consecutive months (ie, has had menses at any time in the preceding 24 consecutive months) must agree and meet the following conditions below (Note: amenorrhea following previous anticancer therapy does not rule out childbearing potential):
 - Medically supervised (ie, performed in a clinic) pregnancy tests with a sensitivity of at least 25 mIU/mL must be conducted in FCCBP/FCBP, including those who commit to true abstinence*. Two pregnancy tests must be conducted prior to starting pomalidomide. The first pregnancy test must be performed 10 to 14 days prior to the start of pomalidomide and the second pregnancy test must be performed within 24 hours prior to starting pomalidomide.

NOTE: The pregnancy test 10 to 14 days prior to initiation of pomalidomide may be omitted, at the discretion of the investigator, for any FCCBP/FCBP who has high acuity disease requiring immediate treatment with pomalidomide. The pregnancy test within 24 hours prior to the first dose of pomalidomide is required to be performed.

The subject may not receive pomalidomide until the Investigator has verified that the results of these pregnancy tests performed on Cycle 1, Day 1 are negative. Female children of childbearing potential/females of childbearing potential with regular or no menstrual cycles must agree to have pregnancy tests weekly for the first 28 days study participation, every 28 days while on study, at study treatment discontinuation visit, and at Day 28 following pomalidomide discontinuation. If menstrual cycles are irregular, the pregnancy testing must occur weekly for the first 28 days of study participation and then every 14 days while on study, at study treatment discontinuation visit, and at Days 14 and 28 following pomalidomide discontinuation.

- Female subjects must, as appropriate to age and at the discretion of the study Investigator, either commit to true abstinence* from heterosexual contact (which must be reviewed on a monthly basis) and/or agree to the use of two reliable forms of approved and effective contraceptive methods simultaneously. The two methods of reliable contraception must include one highly effective method (ie, oral, injectable, or implantable hormonal contraceptive; tubal ligation; intrauterine device; vasectomized partner) and one additional effective barrier method (ie, male condom, diaphragm, cervical cap) 28 days prior to starting pomalidomide, throughout the

entire duration of study treatment including dose interruptions and 28 days after discontinuation of pomalidomide.

Note: Only a progestin-suppressing ovulation pill is acceptable as an oral contraceptive. Copper intrauterine devices are not recommended.

- All male and female subjects must follow all requirements defined in the pomalidomide Pregnancy Prevention Program.

18. Male subjects must, as appropriate to age and the discretion of the study physician:

- Practice true abstinence* (which must be reviewed on a monthly basis) or agree to use a condom during sexual contact with a pregnant female or a FCBP while participating in the study, during dose interruptions and for at least 28 days following pomalidomide discontinuation, even if he has undergone a successful vasectomy or practices complete abstinence.

*True abstinence is acceptable when this is in line with the preferred and usual lifestyle of the subject. Periodic abstinence (eg, calendar, ovulation, symptothermal, postovulation methods) and withdrawal are not acceptable methods of contraception.

19. **For subjects screened/enrolled in France only:** Subject must be affiliated with a Health Insurance Scheme or be a beneficiary of one.

4.3. Exclusion Criteria

The presence of any of the following will exclude a subject from enrollment:

1. Subject has a history of non-central line related thrombosis (arterial or venous), more than one prior central-line related thrombosis (excluding small clots in central lines that are resolved with tissue plasminogen activator [tPA] flush) or known coagulopathy.
2. Subject has first degree family member with a known hereditary coagulopathy.
3. Subject is actively on anticoagulation therapy.
Note: The use of tPA to flush subject's central-line is allowed.
4. Subject has had major (per Investigator discretion) surgery, with the exception of tumor resection, within 21 days from first dose of study drug.
5. Subject has previously received (presence of any of the following will exclude a subject from enrollment):
 - Any prior treatment with pomalidomide. Subjects who have prior treatment with other immunomodulatory compounds (thalidomide, lenalidomide) ARE eligible if they meet all other eligibility criteria and did not have allergic reactions or other "significant toxicity" per Investigator discretion associated with lenalidomide or thalidomide use.
 - Myelosuppressive chemotherapy, immunotherapy, or any investigational agent: ≤ 21 days (≤ 42 days if a nitrosourea) prior to screening.
 - Biological (anti-neoplastic) therapy: ≤ 7 days prior to screening.

- Immunomodulatory therapy (ie, thalidomide, lenalidomide): ≤ 28 days prior to screening.
 - Monoclonal antibody treatment and agents with known prolonged half-lives: < 3 half-lives have elapsed or ≤ 28 days prior to screening, whichever is longer.
 - Prior radiation:
 - Cranial irradiation, total body irradiation (TBI), or ≥ 50% radiation of pelvis: ≤ 3 months prior to screening.
 - Focal irradiation: ≤ 3 weeks prior to screening if radiation field involved a non-target lesion; ≤ 6 weeks prior to screening if radiation field involved a target lesion.
- Note:** True disease progression following prior irradiation therapy must be confirmed by Investigator prior to screening.
- Bone marrow transplant:
 - Presence of graft versus host disease (GVHD)
 - < 6 months since allogeneic bone marrow transplant prior to screening.
 - < 3 months since autologous bone marrow/stem cell transplant prior to screening.
 - < 3 months since stem cell transplant (SCT) or Rescue without TBI with no evidence of GVHD prior to screening.
 - Radioisotopes: fluorothymidine (¹⁸FLT) ≤ 72 hours prior to first dose of study drug
6. Subject has received therapy with a known moderate to potent CYP1A2 inhibitor within 14 days or 5 half-lives of first dose of study treatment (whichever is longer). The treating Investigator should consult a current drug information reference for a complete list (<http://medicine.iupui.edu/clinpharm/ddis/main-table/>).
 7. Subject has received colony-stimulating growth factor(s) within 7 days prior to screening (or within 14 days if subject received polyethylene glycol formulations).
 8. Subject is pregnant, breast-feeding or lactating.
 9. Subject has an untreated or uncontrolled infection defined as ongoing signs/symptoms related to the infection without improvement despite appropriate antibiotics, antiviral therapy and/or other treatment.
 10. Subject has active infectious hepatitis, type A, B, or C, or chronic carriers of hepatitis C. Note: Hepatitis B serological status must be known prior to enrollment. If unknown at screening, a Hepatitis B serology test **must** be performed.
 11. Subject has any prior history of malignancies, other than high-grade glioma, medulloblastoma, ependymoma or DIPG (Note: radiation-associated gliomas are excluded from enrollment)
 12. Subject who, in the opinion of the Investigator, has any significant medical condition, laboratory abnormality, or psychiatric illness that would prevent the subject from participating in the study.
 13. Subject has any condition including the presence of laboratory abnormalities which, in the opinion of the Investigator, places the subject at unacceptable risk if he/she were to participate in the study.

14. Subject has any condition that confounds the ability to interpret data from the study.
15. Subject has symptomatic cardiac disorders (CTCAE v. 4.03 Grade 3 and 4)

CELGENE PROPRIETARY INFORMATION

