9.3. Sample Size and Power Considerations

Under Simon's Optimal two-stage design with a 5% significance level and 90% power, assuming a lower boundary of interest in the response rate of 10% and an upper boundary of interest in the

response rate of 40%, a total of 20 subjects evaluable for the primary endpoint (ie, Response Population) are required per stratum; 9 per stratum in Stage 1 and an additional 11 per stratum in Stage 2.

Enrollment will proceed as follows:

1. Stage 1: Nine subjects will be enrolled into each of the strata.
2. Stage 2: If during Stage 1, ≥ 2 subjects in a given stratum achieve either an OR (either CR or PR) within the first 6 cycles of treatment (within 3 cycles for DIPG) or a long-term SD, an additional 11 subjects shall be enrolled to that stratum; otherwise no additional subjects will be enrolled.
3. If a total of 5 or more subjects across all 20 subjects in a given stratum (Stage 1 and 2) evaluable for the primary endpoint are observed as having either an OR (either CR or PR) within the first 6 cycles of treatment (within 3 cycles for DIPG) or long-term SD, pomalidomide will be considered effective in that disease indication.

Up to 80 subjects (36 subjects in Stage 1 and 44 subjects in Stage 2) will be included should all strata enroll the maximum number of subjects (ie, 20 per stratum), assuming no subjects are replaced.

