9.8. Interim Analysis

For each stratum, there is one interim analysis planned at the end of Stage 1. The interim analysis will be informal, performed internally by Celgene personnel with input, only if needed, from the DMC and steering committee (SC). Enrollment will be suspended for each interim analysis, once the first 9 subjects evaluable for the primary endpoint have been enrolled. Enrollment for each stratum will be re-opened/closed based upon the following criteria:

- Should only one or no subjects be observed as having either an OR (either CR or PR) or a long-term SD, that stratum shall be closed to further enrollment.
- Should at least 2 subjects across Stage 1 have either an OR (either CR or PR) or a long-term SD, then that stratum will continue into Stage 2 to include up to 11 more additional subjects evaluable for the primary endpoint.

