Appendix B: Tumor Response Categories for Target and Non-target Lesions

Target Lesions

For the purpose of this study, response criteria for target lesions are defined as follows:

- **Complete Response (CR):**
 - Complete disappearance on MRI of all measurable lesions.
- **Partial Response (PR):**
 - A reduction of $\geq 50\%$ in tumor size by bi-dimensional measurement (taking as reference the baseline measurements) quantified by the sum of the products of the perpendicular diameters of measurable lesions.
- **Stable Disease (SD):**
 - A decrease of $< 50\%$ or an increase of $< 25\%$ in the sum of the products of the perpendicular diameters of measurable lesions and no evidence of new lesions. Response does not meet the criteria for CR, PR or PD.
- **Progressive Disease (PD):**
 - $\geq 25\%$ increase in the bi-dimensional measurement as quantified by the sum of the products of the largest diameters of the measurable lesions taking as a reference the smallest disease measurement recorded since the start of protocol therapy (nadir).

Non-target Lesions

For the purpose of this study, response criteria for non-target lesions are defined as follows:

- **Complete Response (CR):**
 - Disappearance of all non-target lesions.
 - If spine MRI and/or lumbar CSF cytology were previously positive, it must be negative at time of assessment.
- **Incomplete Response/Stable Disease (IR/SD):**
 - The persistence of non-target lesions, stable (no progression) or decrease in size.
 - If spine MRI and/or lumbar CSF cytology were previously positive at baseline and remains positive with no other evidence of PD.
- **Progressive Disease (PD):**
 - The appearance of one or more new lesions and/or unequivocal progression of existing non-target lesions.
 - If spine MRI and/or lumbar CSF cytology were previously negative and became positive.

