4.4. Overall Study Design and Plan

[figure not shown]
Each tumor type/disease indication incorporates the Simon's Optimal Two-stage study design incorporating the following parameters: significance level of 5%, 90% power and a lower and upper boundary of interest of 10% and 40%, respectively, of the primary endpoint. Based on these boundaries, each tumor type/disease indication will enroll up to 20 subjects eligible for the primary endpoint; 9 in stage one and 11 in stage two. Subjects not eligible for the primary endpoint, ie, not contained within the Response Population, If the number of subjects observed with either an OR or long-term SD according to central response review is ≥ 2 , then enrollment shall continue into stage two; otherwise enrollment will close to that specific tumor type/disease

indication. At the end of stage two, if ≥ 5 out of 20, ie, the target ORSDR $\geq 25\%$, of the subjects enrolled across stage one and stage two combined are observed as having an OR or long-term SD then the treatment will be declared positive in that given tumor type/disease indication; otherwise the treatment will be considered negative in that given tumor type/disease indication (

Figure 2).

If, in a given tumor type/disease indication, by the time the eighteenth subject becomes evaluable for the primary endpoint and only two subjects have been observed across stage 1 and stage 2 combined as having either a OR or long-term SD then enrollment to that tumor type/disease indication will be stopped due to a lack of efficacy.

Figure 1: Overall Study Design

[figure not shown]

ICF=informed consent form, IAF=informed assent form, MRI=magnetic resonance imaging, OS=overall survival, PD=disease progression, PFS=progression-free survival, SAE=serious adverse event, SPM=second primary malignancy.

*From last subject enrolled

**Subjects without a PD at time of treatment discontinuation will continue to be followed for MRI tumor assessment (every 6 months for the first year from treatment discontinuation, then annually thereafter).

Figure 2: Simon’s Optimal Two-stage Parallel Phase 2 Study Design

DIPG=diffuse intrinsic pontine glioma, OR=objective response, PD=progressive disease, LTSD= Long-term stable disease.

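### Tumor resection is allowed in the 21 days before first dose, but no rule requires the baseline MRI to follow it, so debulking could be scored as a partial response

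*Protocol*

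**What the plan says.** **Surgery.** Protocol Section 4.3, Exclusion 4, applies to the following: "Subject has had major (per Investigator discretion) surgery, with the exception of tumor resection, within 21 days from first dose of study drug". The exemption for tumor resection has no time limit of its own. The same section does set an interval for another local treatment: focal irradiation of a target lesion must be more than 6 weeks before screening.

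**Baseline scan.** Inclusion 7 asks for a brain MRI and a "spine MRI with contrast (ie, gadolinium) within 21 days prior to first dose of study treatment". For subjects on steroids, the dose must have been stable or falling for at least 5 days. Sections 3.1, 6.1, 6.4.1 and 6.4.1.1 and Table 4 repeat the 21-day window. All of them count back from first dose, and none mentions surgery.

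**Measurable disease.** Inclusion 6 and Section 6.4.1.1 require measurable disease, and state that this covers subjects resected before enrollment. They do not say which scan must show it.

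**Scoring.** In Appendix B, PR is a reduction of at least 50% "in tumor size by bi-dimensional measurement (taking as reference the baseline measurements"). PD is judged against the smallest measurement, at baseline or later (Section 6.4.1.3). No confirmatory scan is required for PR, and SAP Section 6.1.1 counts PR as best response. Under Section 6.4.1.7, a subject with neither response nor progression by the end of Cycle 6 (Cycle 3 for DIPG) counts as long-term SD.

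**Baseline in the SAP.** The general convention in Appendix A1 takes the latest value on or before the first dose date.

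**The concern.** The endpoint compares tumor area with a reference scan, so anything other than the drug that shrinks the tumor between that scan and the first on-treatment scan is credited to the drug. Resection is the most direct example, and the protocol allows it inside the scan window. A pre-operative reference has two effects. It can turn an unchanged or growing residual into a PR. It also sets the PD reference too high at the first on-treatment scan, so that regrowth may be read as stability.

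The decision rules make a single case matter. A stratum opens Stage 2 on 2 successes in 9 and is called effective on 5 in 20. With no control arm, nothing would reveal the error.

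**Working it through.** **1. Does any text set the order of scan and resection?** Take an MRI on Day -20, partial resection on Day -10 and first dose on Day 1. The scan is inside 21 days, and Exclusion 4 exempts the operation. Enrollment is on Cycle 1 Day 1 (Table 4, Section 6.2), so this resection falls before enrollment and Inclusion 6 applies to the subject. That criterion requires measurable disease but does not tie it to a post-operative image. The Day 1 re-confirmation of eligibility is described in Section 6.2 as safety assessments, and no MRI is scheduled for it. Table 4 footnote a asks for re-evaluation as needed after a change in clinical status and does not name surgery. No text sets the order.

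**2. Effect on the reading (pre-operative area = 1.00; removal fractions assumed).**
- 60% removed leaves 0.40. Unchanged, this reads -60% against the pre-operative scan (PR), but 0% against a post-operative scan (SD).
- After 25% regrowth: 0.40 × 1.25 = 0.50. This reads -50% (PR, exactly at the threshold) instead of +25% (PD).
- After 50% regrowth: 0.40 × 1.50 = 0.60. This reads -40% (SD) instead of +50% (PD).
- 30% removed leaves 0.70. PD is called at the first scan only from 1.25/0.70 = 1.786, so growth of up to 78% passes there.

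**3. The plan's own design.** Protocol Section 9.3 sets the design "with a 5% significance level and 90% power", and SAP Section 4.4 gives "a lower and upper boundary of interest of 10% and 40%, respectively, of the primary endpoint". The sizes are "9 per stratum in Stage 1 and an additional 11 per stratum in Stage 2". The Stage 1 rule is in Section 9.8: "Should at least 2 subjects across Stage 1 have either an OR (either CR or PR) or a long-term SD". The final rule is 5 or more of 20.

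P(effective) = Σ over x ≥ 2 of P(X = x; 9, p) × P(Y ≥ 5 - x; 11, p)

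At p = 0.10, P(Y ≥ 3) = 0.0896, P(Y ≥ 2) = 0.3026 and P(Y ≥ 1) = 0.6862:

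| Stage 1 successes | Probability | × Stage 2 | Product |
|---|---|---|---|
| 2 | 0.1722 | 0.0896 | 0.0154 |
| 3 | 0.0446 | 0.3026 | 0.0135 |
| 4 | 0.0074 | 0.6862 | 0.0051 |
| ≥ 5 | 0.0009 | 1 | 0.0009 |
| Total | | | **0.0349** |

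At p = 0.40 the same sum gives 0.902. The stated design reproduces, and the sample size is not in question.

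**4. One such subject in Stage 1, all others at 10%.** Let s be the probability that this subject is scored a success.
- If certain (s = 1), the other 8 must supply at least 1 success, and the final rule needs 4 more in all: 0.3826 × 0.0896 + 0.1488 × 0.3026 + 0.0331 × 0.6862 + 0.0050 = 0.107.
- If certain to fail (s = 0): since 0.0349 = 0.10 × 0.107 + 0.90 × B, B = 0.0269.
- In general, P = s × 0.107 + (1 - s) × 0.0269.

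| s | False-positive chance |
|---|---|
| No such subject | 3.5% |
| 0.25 | 0.0268 + 0.0202 = 4.7% |
| 0.5 | 0.0535 + 0.0135 = 6.7% |
| 1 | 10.7% |

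The chance of opening Stage 2 is 0.225 without such a subject and 1 - 0.9^8 = 0.570 with s = 1.

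**5. One certain success in each stage.** Eight others remain in Stage 1 and ten in Stage 2, with P(Y ≥ 2; 10) = 0.2639 and P(Y ≥ 1; 10) = 0.6513: 0.3826 × 0.2639 + 0.1488 × 0.6513 + 0.0381 = 0.236.

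**The case against.** The strongest reply is that the protocol already means a post-operative scan. Inclusion 6 speaks directly to resected subjects, and a pre-operative image cannot show what disease remains. Inclusion 7 gives the scan's purpose as recording the extent of tumor at baseline. Section 6.1.5 has the site confirm at enrollment that all criteria still hold. Exclusion 14 removes subjects whose condition would confound the data. If a post-operative, pre-dose MRI exists, the SAP convention already makes it the baseline. Endpoints rest on central review, and the Imaging Manual and review charter, which are not among these documents, may contain a rule.

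Most of this stands. It shows intent and narrows the gap to subjects with no post-operative scan. It does not close the gap, because none of these texts states the order and the two outside documents cannot be relied on here.

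A reader might go further and infer three things that the documents do not support:
- **That the Day -20/Day -10 subject clearly meets every criterion.** Inclusions 6 and 7 can fairly be read against that.
- **That such a subject is a near-certain success.** Table 10 (Appendix C) also requires a stable or improved neurologic examination, steroids no higher than baseline and no new lesion. The PR route needs a large resection and little regrowth by Cycle 3 Day 1, which is 56 + 10 = 66 days after a Day -10 operation.
- **That any debulking yields long-term SD.** Outside DIPG, the first on-treatment scan can become the nadir, and a rise of 25% from it at Cycle 5 or 7 is PD. SAP Section 6.1.1 also requires 6 completed cycles. The SD route matters mainly in DIPG, where one scheduled brain MRI at Cycle 4 Day 1 decides. The documents do not say how often DIPG subjects are resected.

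**Conclusion.** The gap is real but narrow. The stated rules let a pre-operative MRI serve as the reference when a resection falls between that scan and first dose and no later scan is taken. The main consequence is a PR credited to surgery.

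The increase from 3.5% to between 4.7% and 10.7%, and the 23.6% for one certain success in each stage, are conditional figures. They assume that such subjects occur in the stratum, that every other subject succeeds at 10%, and that s takes the values shown. The documents give neither a frequency nor a value for s, so these figures are not the trial's expected error rate. The point is a low-cost improvement to the wording and leaves the two-stage design as it is.

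**What to change.** Add to Inclusions 6 and 7 and to Section 6.4.1.1: the baseline MRI must be obtained after the most recent tumor resection, within the existing 21-day window before first dose, and measurable disease must be confirmed on that scan.

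Add a data check that compares the resection date with the baseline scan date. The SAP (Section 8.4.1) already lists an eCRF page for prior cancer surgeries.

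Sample size, decision rules and surgical eligibility stay as they are. The cost is an occasional repeat MRI for a subject who has no post-operative scan.
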